7.5 Termination Criteria

Upon occurrence of any one of the events listed below, the study will terminate or be modified accordingly:

- Completion of the study by a sufficient number of subjects (294 subjects) to reach our confidence level
- Termination of Arm 1: Serious adverse event due to treatment with Proxalutamide
- Substantial evidence of treatment difference between the arms. The study design will be modified to an open-label study.

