3.6 Discontinuation

In the event that a subject experiences a SAE or an AE grade 3 or 4 (defined in Section 6) we will discontinue the study for that particular subject.

In the event a subject in any arm experiences a SAE defined as death not due to respiratory failure (presents with clear lung CT and no ARDS symptoms) the study will be discontinued. The remainder of the study shall continue.

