6.3.2 Definition of Serious Adverse Event (SAE)

An SAE is defined as “An AE or suspected adverse reaction is considered serious if, in the view of either the investigator or the sponsor, it results in any of the following outcomes: Death, a life-threatening AE, inpatient hospitalization or prolongation of existing hospitalization, a persistent or significant incapacity or substantial disruption of the ability to conduct normal life functions, or a congenital anomaly/birth defect. Important medical events that may not result in death, be life-threatening, or require hospitalization may be considered serious when, based upon appropriate medical judgment, they may jeopardize the patient or subject and may require medical or surgical intervention to prevent one of the outcomes listed in this definition. Examples of such medical events include allergic bronchospasm requiring intensive treatment in an emergency room or at home, blood dyscrasias or convulsions that do not result in inpatient hospitalization, or the development of drug dependency or drug abuse.” “Life-threatening” refers to an AE that at occurrence represents an immediate risk of death to a subject. An event that may cause death if it occurs in a more severe form is not considered life-threatening. Similarly, a hospital admission for an elective procedure is not considered a SAE. All SAEs, as with any AE, will be assessed for severity and relationship to study intervention. All SAEs will be recorded on the appropriate SAE CRF. All SAEs will be followed through resolution or stabilization by a licensed study physician (for IND studies, a physician listed on the Form FDA 1572 as the site PI or Sub-Investigator). All SAEs will be reviewed and evaluated by DMID and will be sent to the SMC (for periodic review), and the IRB/IEC.

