6.3.6 Relationship to Study Intervention

For each reported adverse reaction, the PI or designee must assess the relationship of the event to the study product using the following guideline:

Related – The AE is known to occur with the study intervention, there is a reasonable possibility that the study intervention caused the AE, or there is a temporal relationship between the study intervention and event. Reasonable possibility means that there is evidence to suggest a causal relationship between the study intervention and the AE.

Not Related – There is not a reasonable possibility that the administration of the study intervention caused the event, there is no temporal relationship between the study intervention and event onset, or an alternate etiology has been established.

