6.3.7 Time Period and Frequency for Event Assessment and Follow-Up

For this study, all Grade 3 and 4 AEs and all SAEs occurring from the time the informed consent is signed through the Day 28 (end of study) visit will be documented, recorded, and reported.

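### Sections 3.6, 6.3.6 and 7.5 cannot be applied consistently: one on-treatment SAE can be both Related and Not Related, and 7.5 does not say which meaning stops Arm 1

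*Combined protocol and SAP*

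**What the plan says.** All references are to the current protocol, the version that covers men and women.

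- **7.5 Termination Criteria.** The lead-in reads "Upon occurrence of any one of the events listed below, the study will terminate or be modified accordingly". One listed event is "Termination of Arm 1: Serious adverse event due to treatment with Proxalutamide". No number of events, grade, decision-maker or unblinding step is given, and the causal phrase is not defined or linked to another section.
- **6.3.6 Relationship to Study Intervention.** *Related* has three alternatives, the last being "or there is a temporal relationship between the study intervention and event". *Not Related* also has three, the last being "or an alternate etiology has been established".
- **6.3.2 and 6.3.7.** An SAE includes "Death, a life-threatening AE, inpatient hospitalization or prolongation of existing hospitalization". The protocol collects "all SAEs occurring from the time the informed consent is signed through the Day 28 (end of study) visit".
- **3.6 Discontinuation, paragraph 1.** For any SAE, or any grade 3 or 4 AE, "we will discontinue the study for that particular subject".
- **3.6 Discontinuation, paragraph 2.** For a death in either arm not due to respiratory failure, "the study will be discontinued. The remainder of the study shall continue".
- **3.3 Randomization.** Participants, investigators and the study team stay blinded until the final database lock or the interim analysis.

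**The concern.** Everyone enrolled is already an inpatient at ordinal score 3 to 6, and death is both a scale category and a secondary endpoint. The protocol therefore expects serious events from the disease itself. For each one it must be clear whether the event is attributed to the drug, and whether the consequence falls on the subject, the arm or the study.

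The text does not settle either question. With two arms, ending Arm 1 ends the randomized comparison, so an ambiguous trigger is a risk to the whole trial. If the trigger is instead left to judgement, related-SAE counts depend on which half of 6.3.6 an investigator applies. SUSAR classification (6.3.3) also rests on causality and words the standard differently again, as a reasonable possibility.

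**Working it through.** **Step 1: apply the text to one case.** Take a subject on proxalutamide who dies of COVID-19 respiratory failure on day 8.

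| Section | Result |
|---|---|
| 6.3.2 | SAE, because it is a death |
| 6.3.6, Related | Met: the event follows dosing in time |
| 6.3.6, Not Related | Also met: another cause is established |
| 3.6 paragraph 1 | Consequence for this subject only |
| 3.6 paragraph 2 | Does not apply: the death is respiratory |
| 7.5 | Undetermined: depends on what the causal phrase means, and on knowing the arm, which the study team does not |

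If the death is not respiratory, paragraph 2 of 3.6 applies. It discontinues the study in one sentence and continues its remainder in the next.

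**Step 2: exposure.** Section 7.2 plans 294 subjects per cohort, 147 per arm, so 147 × 2 = 294 subjects on active drug over both cohorts. The plan states no operating characteristic for the termination rule. Its sample-size formula gives 12(1.960 + 1.282)²/(ln 2)² = 262.4, divided by (1 − Σp³). The category probabilities are not in the documents, so 294 cannot be reproduced independently. It is matched at Σp³ = 0.075: 262.4/0.925 = 283.7, and 283.7/0.965 = 294.0. The figure is used here only as exposure.

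**Step 3: chance of at least one qualifying SAE in Arm 1 by full enrolment.** P = 1 − (1 − p)ⁿ, assuming independent subjects with a common rate p. The documents give no SAE rate for hospitalized COVID-19 patients, so a range is needed. The available anchors are:

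- Study 3 (phase 1, 40 men with prostate cancer, mean dosing 87.6 days): 1/40 = 2.5% drug-related SAEs and 9/40 = 22.5% SAEs of any cause. The one drug-related event was at 500 mg/day; there were 0/7 at 300 mg/day.
- The prior outpatient COVID-19 study: 0/134 with drug-related AEs at 200 mg.

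At constant hazard, the Study 3 rates scale as follows:

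- drug-related, 14 days: 1 − 0.975^(14/87.6) = 0.40%
- drug-related, 28 days: 1 − 0.975^(28/87.6) = 0.81%
- any cause, 14 days: 1 − 0.775^(14/87.6) = 3.99%

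| Reading of 7.5 | Rate p | n = 147 | n = 294 |
|---|---|---|---|
| Causal | 0.1% (assumed) | 13.7% | 25.5% |
| Causal | 0.40% (1/40, 14 days) | 44.8% | 69.6% |
| Causal | 0.81% (1/40, 28 days) | 69.6% | 90.7% |
| Causal | 1% (assumed) | 77.2% | 94.8% |
| Causal | 2.5% (1/40, unscaled) | 97.6% | 99.9% |
| Timing alone | 3.99% (9/40, 14 days) | 99.7% | >99.9% |
| Timing alone | 5% (assumed) | 99.9% | >99.9% |

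**Step 4: uncertainty in the anchors.** The exact 95% interval for 1/40 is 0.06% to 13.2%, which gives 9% to nearly 100% at n = 147. The 0/134 result has a one-sided 95% upper bound of 1 − 0.05^(1/134) = 2.2%, which gives at most 96.3% at n = 147. A 95% chance of a trigger needs a qualifying rate of about 2.0% (n = 147) or 1.0% (n = 294).

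**The case against.** A reader might infer that the rule, taken literally, would almost surely end Arm 1 early. The documents do not support that.

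- Section 7.5 does not use the word Related or cite 6.3.6, and its own wording asks for causation. Near certainty needs a link that the protocol does not make.
- If an event meets both categories, the literal text gives no determinate answer. Not Related is as available as Related.
- The probabilities are for at least one event by full enrolment. None of them shows when it would occur, so *early* is not established.
- The 2.5% rate comes from longer dosing and one event at a higher dose, and the closest COVID-19 experience is 0/134.

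A reader might also infer that 3.6 and 7.5 contradict each other outright. They need not. Paragraph 1 of 3.6 covers any SAE at subject level, and 7.5 covers only treatment-caused SAEs at arm level, so they can be read as two tiers. The protocol does not say so, however, or state when an event passes from one tier to the other.

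There is also some oversight. Section 6.3.2 sends SAEs to an SMC for periodic review, and 6.3.9.1 has a medical monitor assess each one, including its effect on protocol conduct. Section 11 has the study monitor hold arm assignments. This narrows the gap, but none of these roles is given the arm-level decision, and 7.5 mentions none of them. The lead-in's allowance for modification helps little, because the Arm 1 item itself says termination.

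What stands is the overlap in 6.3.6, the undefined trigger in 7.5 under blinding, and the self-contradiction in paragraph 2 of 3.6.

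**Conclusion.** The point holds as an inconsistency. The same event can be classified two ways under 6.3.6, the arm-stopping rule does not say which classification it uses, and 3.6 gives a study-level instruction that its next sentence reverses.

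The size depends on the reading. If timing-only Related triggers 7.5, a trigger is near certain, above 99% per cohort at an assumed on-treatment SAE rate of about 4%. On a causal reading it ranges from about 14% to 98% per cohort, and from about 25% to 99.9% over both, for rates of 0.1% to 2.5%. These figures assume independent subjects, a constant hazard where rates are scaled, and cancer patients as a stand-in. The overlap in 6.3.6 and the contradiction in 3.6 do not depend on any of these rates.

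**What to change.** 1. Reword 6.3.6 so that its two categories exclude each other and every event falls into exactly one.
2. State in 7.5 which causality category its trigger means.
3. Reconcile both paragraphs of 3.6 with 7.5, so that subject-, arm- and study-level consequences are distinct and do not conflict.
4. Assign the arm-level decision to a body with unblinded access, such as the SMC already named in 6.3.2.

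The clinical threshold and the direction in which the passages are reconciled are for the sponsor and its safety reviewers.

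The cost is wording in three sections and a short amendment; the sample size does not change. The final statistical plan was written while the manuscript was being drafted and does not address these sections. If conduct is already complete, the report should state how relatedness was assigned and whether the 7.5 rule was ever applied.

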7.6 Accountability Procedure

The data will be analyzed by a bio-statistics expert. The data will also be independently verified by an outside expert consultant.

7.7 Deviation Reporting

No deviation from the plan will be implemented without the prior review and approval of the EC/IRB.

8 Direct Access to Source Data/Documentation

The PI and hospital will permit trial-related monitoring, audits, IRB/IEC(s) review and regulatory inspection(s) by providing direct access to source data/documentation.

9 Quality Control and Quality Assurance

Every effort will be made to keep staff assignments consistent throughout the entire study. The PI who assesses the subject at baseline should follow the subject throughout the completion of the study. This will ensure that this study is conducted – and that data is generated, documented (recorded), and reported - in compliance with this protocol, with GCP, and any other applicable regulatory requirements. The study monitor will audit the study procedures and CRFs throughout the study.

10 Ethical Considerations

This study will be conducted according to US and international standards of Good Clinical Practice (FDA regulations 21 CFR 312 for IND studies and FDA guidance E6) for all studies. Applicable government regulations and hospital research policies and procedures will also be followed.

This protocol and any amendments will be submitted to the Institutional Review Board (IRB) for formal approval to conduct the study. The decision of the IRB concerning the conduct of the study will be made in writing to the investigator.

All subjects for this study will be provided a consent form describing this study and providing sufficient information for subjects to make an informed decision about their participation in this study. This consent form will be submitted with the protocol for review and approval by the IRB. The formal consent of a subject, using the IRB-approved consent form, will be obtained before that subject is submitted to any study procedure. This consent form must be signed by the subject or legally acceptable surrogate, and the investigator-designated research professional obtaining the consent.

11 Data Handling and Record Keeping

During enrollment, each subject will be assigned a number. The numbers will be consecutive starting at 001.

During enrollment a record will be created for each subject. Each record will contain the subject's demographics, subject's efficacy parameters and any adverse events or study related information.

The subjects' records will be stored and handled in the same manner as the PI's patients' records.

The study monitor will keep a separate record at the monitor's office of each subject's identification number, the treatment administered to the subject (arm assignment), outcomes and any laboratory results.

No other data will be recorded. No personal information will be kept outside the study site.

Data compiled at the end of the study will not include any information that can be used to identify individuals.

The site will keep all subject records for a minimum of 3 years after the completion of the study.

12 Finance and Insurance

The Principal Investigator will be responsible for the cost of study. The site carries insurance for accidental injury. There is no other insurance.

APPENDIX 1

Drugs that should be used cautiously with Proxalutamide

Strong CYP3A4 inducer
Avamibe, Carbamazepine, Phenytoin, Rifampicin, Mitotan, Nevirapine, Phenobarbital, Rifabutin, Rifapentine, St. John's wort, Alfentanil, Ryclosporin, Dihydroergotamine / Ergotamine, Fentanyl, Irinotecan, Pimozit, Quinidine, Sirolimus, Tacrolimus
Moderate CYP3A4 inducer
Smacet, Tavern, Bosentan, Efaviron, Etruverin, Lopinavir, Modafinil, Nafceillin, Thalidazine, Tiranavir, Ritonavir
Strong CYP3A4 inhibitor
Posidovir, Clarithromycin, Conivatan, Indinavir, Itraconazole, Ketoconazole, lopinavir / Ritonavir, Mibedil, Nefazodone, Nefenavir, Posaconazole, Ritonavir, Saquinavir, Trapivir, Taliomycin, Voriconazole, Etigavir / Ritonavir, Fluconazole, Tiranavir / Ritonavir, Acetamycin
Moderate CYP3A4 inhibitors
Apronavir, Aripitan, Azanavir, Casopitam, Cimetidine, Ciprofloxacin, Clazotinib, Cyclosporin, Dalunavir, Diltiazem, Dronedarone, Erythromycin, Imatinib, Tofesoyang, Verapamil
Sensitive CYP3A4 substrates
Remifentanil, Aripiptam, Budesonide, Buspirone, Conivatan, Daphnesin, Darunavir, Dasatinib, Dronedarone, Eletroptan, Eplerenone, Everolimus, Felodipine, Indinavir, Fluticasone, Lopinavir, Lovastatin, Lulasidone, Maravelo, Midazolam, Nisoldipine, Quetiapine, Saquinavir, Sildenafil, Simvastatin, Sirolimus, Tolvaptan, Tiranavir, Triazolam, Vardenafil
Narrow therapeutic index CYP3A4 Substrate
Astemizole, Cisapride, Cyclosporine, Dihydroergotamine, Fentanyl, Pethidine, Quinidine, Tacrolimus, Terfenadine
Sensitive CYP2D6 substrates
Tomoxetine, Decipamine, Dextromethorphan, Metoprolol, Nebeprolol, Perphenazine, Tolterodine, Venlafaxine, Avamibe, Carbamazepine, Phenytoin sodium, Rifampicin

Narrow therapeutic index CYP2D6 Substrate

Thioridazine

Revision History				
Revision	Description of Change		Date	Signature
1	New draft release	[name]	Dec 27, 2020	
2	Amendments to end points	[name]	Dec 29, 2020	
3	Amended AE section	[name]	Dec 30, 2020	
4	Amended to include female cohort	[name]	Jan 10, 2021	
5	Final review for female cohort	[name]	Jan 10, 2021	
6	Added exclusions for sexual activity and minor corrections	[name]	Jan 11, 2021	
7	Changed randomization model	[name]	Jan 19, 2021	
8	Amended inclusion criteria	[name]	February 1, 2021	

CONFIDENTIAL

This material is the property of the Applied Biology Inc. Do not disclose or use except as authorized.

FINAL STATISTICAL PLAN WITH SUMMARY OF CHANGES FROM THE FINAL PROTOCOL

We had to make minor adjustments to the statistical plan of the final protocol while writing the manuscript to make the statistical plan more stringent and clearer. The rationale for each change or no change is also presented.

Table of contents:

1. Primary Outcome Measure.....	1
2. Secondary Outcome Measures	2
3. General principles.....	4
4. Statistical hypothesis	5
5. Primary analysis efficacy.....	6
6. Sample size calculation	7

1. Primary Outcome Measure

Proposed in the final protocol	Final statistical Plan	Rationale
Treatment efficacy of proxalutamide relative to placebo arm as assessed by the COVID-19 ordinal scale [time frame: day 14]	No change	The distribution analysis of all the COVID-19 8-point ordinal scale scores at day 14 covers all possible scores, 1 to 8. This is better illustrated graphically for group comparison.
No specific measure of effect was appointed for the Primary efficacy analysis (quantitative efficacy measure).	Recovery ratio was defined as the measure of effect for the primary outcome. The treatment efficacy of proxalutamide was assessed by the proportion of recovered patients in both study arms [time frame: 14 days]. Recovery was defined as reaching scores 1 and 2 in the COVID-19 ordinal scale	Scores 1-2 represent a clear cut for recovery (alive hospital discharge).

2. Secondary Outcome Measures

As proposed in the final protocol	Done in the final statistical Plan	Rationale
Treatment efficacy of Proxalutamide relative to placebo arm as assessed by the COVID- 19 ordinal scale (defined in Section 5.1) [Time Frame: Day 28]	A clear cut-off point was used in the COVID-19 scale (scores 1 and 2) so that we were able to measure the effect size recovery ratio [time frame: 28 days].	All scores at Day 28 are informative and is better presented in a graph. As reported for the primary outcome, we clarified a measure of effect within this secondary outcome measure.
Time to recovery [Time Frame: Day 1 through Day 28] Recovery is defined as the first day on which the subject satisfies one of the following two categories from the ordinal scale.1): 2) Not hospitalized, limitation on activities and/or requiring home oxygen; 1) Not hospitalized, no limitations on activities.	Name changed to post-randomization time to recover/alive hospital discharge [time frame: day 1 to day 28] in median days (interquartile range). Recovery was defined as the first day on which the subject reached scores 1 and 2 in the COVID-19 ordinal scale.	We needed to be more specific in this outcome to make it clearer and reproducible.
Proportion of death [Time Frame: Day 1 through Day 28] Defined as the number of subjects who have died in each arm divided by the numbers of subjects randomized to the treatment arm	Name changed to 28-day all-cause mortality rate . The proportion of patients who reached score 8 in the 19-COVID ordinal scale after randomization. [Time frame: 28 days]	The outcome is still the same described in the statistical plan of the final protocol, however we just clarified that it refers to all-cause mortality. All-cause mortality is a more stringent measure, and therefore this change goes against the direction of the bias. Although mortality at 14 days could be contemplated in the original Primary outcome (score 8), we decided to analyze mortality at 28 days only, which is more stringent and reflects the intention-to-treat.
Duration of new oxygen use [Time Frame: Day 1 through Day 28]	Excluded	This outcome measure was not adequately reported by the hospital sites, and therefore we have not included it in the final statistical plan.
Proportion of subjects testing positive for SARS-CoV-2 [Time Frame: Day 14]	Excluded	This outcome also needed to be abandoned because we lacked financial resources to test all patients again for SARS-CoV-2 at day 14.
Subgroup analysis based on: 1) age stratification; and 2) androgen status as defined by “Gabrín sign” or “PCOS signs” will be conducted for the primary and secondary outcomes.	Changed to include the subgroup analysis per 1) baseline score (severity of the disease), 2) gender and 3) hospital site. No hypothesis testing was performed in these subgroup analyses to avoid finding significant p-values by chance due to multiple comparisons. Androgen status was excluded from the subgroup analysis.	Several reasons led us to make these new subgroup analyses: 1. Age was lower than expected, lower age cut-offs did not show relevant findings to be reported, possibly in the future we may plan for a multivariate analysis with factors such as women post-menopause. Also, pre-determining age cut-offs for analyses were needed. Age

		
distribution graphs were included in the supplement.
 
2. Since the randomization scheme was changed in the small hospital located in the remote Amazon areas to control for sharing and unblinding in these regions (see randomization details in the supplement), we needed to evaluate if there was interaction between the overall effect size [recovery ratio, and all-cause mortality ratio] per city of sites. Important to say here that in the hospital centers located in the capital of the state of Amazonas, randomization scheme was performed as planned.3. Since men are by definition more androgenic it was important to evaluate the effects specifically.4. Finally, we checked if there were an interaction effect between the patients with more severe presentations such as baseline score 6 compared to 5, 4, 3.
--	--	-------------------------------------------------------------------------------------------------------------------------------------------------------------------------------------------------------------------------------------------------------------------------------------------------------------------------------------------------------------------------------------------------------------------------------------------------------------------------------------------------------------------------------------------------------------------------------------------------------------------------------------------------------------------------------------------------------------------------------------------------------------------------------------------------------------------------------------------------------------------------------------------------------------------------

3. General principles

As proposed in the final protocol	Done in the final statistical Plan	Rationale
Continuous variables will be expressed as median (interquartile range [IQR]) and categorical variables will be expressed as a number	Continuous variables were expressed as median (IQR) and categorical variables were expressed as a number and in a risk percentage.	Expression of the categorical variables only as a number is not sufficient to allow for calculation of risk ratios. Then, absolute risk ratios were calculated for primary (14-day Overall Recovery rate) and secondary outcomes (28-day recovery rate and 28-day all-cause mortality)
95% confidence intervals will be calculated for the primary outcome	95% confidence intervals will be calculated for the primary outcome, secondary outcomes and subgroup analysis.	All secondary outcomes expressed in ratios were reported along with the 95% confidence interval to allow for a better understanding of the effect sizes.
Group comparisons will be analyzed by the Wilcoxon rank sum test or χ^2 test	For all categorial effect sizes, hypothesis testing was performed with the χ^2 test, including risk ratios. 95% Confidence intervals were reported in results tables, for the primary endpoint Overall Recovery Ratio), along with the P value. For the Adverse AE table, P-values were included. Other outcomes described as median and IQR were compared with the Wilcoxon rank sum test.	The primary hypothesis testing previously stated was maintained. However, we explained in which cases the different tests were applied to increase transparency.
Differences between rates of clinical improvement will be calculated using unadjusted ordinal logistic regression or Cox proportional hazard models	We used Kaplan-Meier's survivor function for estimates of proportion surviving, and failure function for estimates of alive hospital discharges. Cox proportional hazards model was kept only to calculate hazard ratio (HR) for death and its 95% confidence interval (CI). Graphical assessment and Kaplan-Meier versus predicted survival showed that of the proportional-hazards assumption has not been violated	For better demonstration of the 95% CI and timeline of the evolution of the outcomes in figures. For measure of effect, as stated in the Primary and Secondary outcomes, we adopted relative risk (or Risk Ratio) for easier understanding.
Statistical analyses will be conducted using XLSTAT version 2020.5.1 (Addinsoft, Inc.)	Statistical analysis was conducted using Stata/SE version 16.1 for Mac (StataCorp LLC, College Station, TX, USA).	Preference of the team performing statistical analysis

4. Statistical hypothesis

As proposed in the final protocol	Done in the final statistical Plan	Rationale

The primary endpoint is the distribution of clinical assessments on the COVID-19 ordinal scale at day 14. The primary outcome will be analyzed using the Wilcoxon rank sum test.
	
The primary efficacy endpoint was described as the overall 14-day recovery ratio. This effect measure was obtained after dichotomization of the COVID-19 ordinal scale for scores 2 and 1, representing patients that were discharged from hospital.
	
Although the distribution is still presented graphically, and tested for statistical significance, a clear cut-off point in the COVID-19 ordinal scale was used to obtain the Overall Recovery Ratio. Recovery ratio is a clinically meaningful effect measure.


The Null Hypothesis (H0) is that the distribution of clinical assessments on the COVID-19 ordinal scale at day 14 among hospitalized COVID-19 subjects treated with Proxalutamide is equal to the distribution of clinical assessments on the COVID-19 ordinal scale at day 14 among hospitalized COVID-19 subjects treated with the Proxalutamide placebo
	
The null hypothesis applied to the primary endpoint Overall Recovery Ratio is that there is no association between the recovery risk rates of the study arms and the type of treatment (proxalutamide or placebo) in the hospitalized patients with COVID-19
	
Since the primary outcome was refined with a clear efficacy endpoint, defined as a binary measure, the null hypothesis was rephrased to be in line with the chi-square test.

The Alternative Hypothesis (HA) is that the distribution of clinical assessments on the COVID-19 ordinal scale at day 14 among hospitalized COVID-19 subjects treated with Proxalutamide is not equal to the distribution of clinical assessments on the COVID-19 ordinal scale at day 14 among hospitalized COVID-19 subjects treated with the Proxalutamide placebo
	
The alternative hypothesis applied to the primary endpoint Overall Recovery Ratio is that there is an association between the recovery risk rates of the study arms and the type of treatment (proxalutamide or placebo) in the hospitalized patients with COVID-19, meaning that the experimental treatment may affect the Overall Recovery Ratio.
	
The primary outcome was refined with a clear efficacy endpoint, defined as a binary measure the alternative hypothesis was rephrased to be in line with the chi-square test.

5. Primary analysis efficacy

As proposed in the final protocol	Done in the final statistical Plan	Rationale

The non-parametric Wilcoxon rank sum test (Mann Whitney U) will be used to assess the primary end point. P-values <0.05 will be considered significant. All statistical analysis will be based on the intent-to-treat (ITT) population. All missing data will be described.
	
The non-parametric Wilcoxon rank sum test was used to assess some of the secondary outcomes described above.
 
The intention-to-treat protocol was performed in the final analysis. Missing data was reported.
	
The primary outcome was refined with a clear efficacy endpoint, defined as a binary measure, and thus, Wilcoxon Rank Sum test was not appropriate for such type of variable.


No measure of effect
	
Included measure of effect: Overall Recovery Ratio [time frame: 14 days]
	
Although we meant to calculate the overall recovery ratio, the outcome was not clearly described in the statistical plan of the protocol, and sample size was based on odds ratio for recovery.

6. Sample size calculation

As proposed in the final protocol	Done in the final statistical Plan	Rationale

The sample size estimation is based on the results reported in the placebo arm of the Adaptive COVID-19 Treatment Trial (NCT04280705) protocol scenario 4: On day 15, 61% of subjects in NCT04280705 placebo group remained hospitalized. For 90% power to detect an odds ratio of 2.0 using a two-tailed test with a type I error rate of 5%, and 3.5% of the subjects will not complete the study based on NCT04280705
	
No change.
 
However, we noticed that the way the sample size estimation was described may be hard for many readers to follow it.
 
An odds ratio for improvement of 2 over a baseline recovery risk of 39% (NCT04280705, scenario 4), results in a difference of 14% in the absolute recovery rate. The sample size was calculated to be able to detect a difference of 14% in Overall Recovery Rate at 14 days (risk ratio of 1.36) with a power of 90% and a type I error of 5%, over the estimated 39% recovery rate for the placebo group, and 3.5% non-compliance/cross over in the study groups.
	
Although no change was done in the sample size estimate, we rewrote it using simpler and more direct terms.

Sample size estimate: Based on the assumptions above, we calculated that at a minimum we would need to recruit for each cohort 294 subjects (147 subjects in each arm) i.e., a total of approximately 600 subjects.
	
No change
	
We verified that the sample size was still 90% powered after inclusion of baseline score 6 to the final protocol.

These minor changes in the statistical analysis plan were performed while writing the manuscript.

Researchers involved in the statistical analysis that implemented the changes:

[name], MD, PhD

[name], DDS, PhD
